7.4. Dose Modification

7.4.1. Dose Decision/Escalation

Safety data (see below) will be the primary criteria for the dose escalation. The available PK data for LY3303560 obtained during the study may be used to assist in dose escalation decisions but these data are not required for every decision. No dose escalation can occur without prior discussion between investigator(s) and the Lilly clinical pharmacologist/CRP. In the case of disagreement, the decision of the investigator(s) will be followed, except in a situation where Lilly's proposal is the more conservative action (for example, where the investigator wishes to escalate and the Lilly clinical pharmacologist/CRP does not) in which case, the Lilly proposal will be followed.

Safety data (including MRI scans) up to Day 85 from the minimum number of subjects (see Section 5.1.3) will be reviewed by the sponsor and investigator(s) to determine if the current dose was well tolerated and the proposed dose level for the next cohort is appropriate (see Section 10.3.6). The safety data reviewed will include AEs, ECGs, vital signs (blood pressure and pulse rate), MRIs, neurological examinations, C-SSRS, and safety laboratory tests. See Section 5.1.4 for details of the dose escalation for Japanese patients.

Safety data, in particular TEAEs, SAEs, and adverse laboratory abnormalities, will be independently assessed by the investigator, and will be considered related to the IMP unless there is clear evidence that the event is not related.

After review of these data, an agreement on the appropriate dose for the next cohort will be made by the investigator(s) and sponsor. For doses above 70 mg, the dose level of LY3303560 selected should also have been shown to be well tolerated with no safety concerns when administered as a single dose in the ongoing LMDA study, prior to initiating dosing at that dose level in this study.

If any of the following scenarios occur, dosing at the current level and further dose escalation will be discontinued:

- 1) One or more patient experiences an SAE that is considered related to LY3303560 administration
- 2) Two or more patients experience a clinically significant event (CSE) that is considered related to LY3303560 administration. (A CSE will be defined as a moderate-to-severe AE, abnormal clinical sign, or clinical laboratory finding that may pose a risk to the well-being of the subject)
- 3) Two or more patients at a dose level experience moderate or severe AEs that impair normal activities, and are considered related to LY3303560, but do not meet the CSE criteria

- 4) After the introduction of premedication in accordance with the protocol, 2 or more patients develop (according to Common Terminology Criteria for Adverse Events [CTCAE]) \geq Grade 2 acute AEs related to the infusion, during the infusion or within 2 hours of completion, that do not resolve with a reduced infusion rate and/or supportive care.

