5.1.3. Treatment Phase

Each cohort will consist of 8 patients randomised (6 LY3303560: 2 placebo) to a 25-week MAD treatment period (7 doses), after which they will be given the option of continuing the treatment up to 49 weeks (up to 6 further doses, Visits 14 to 19). Patients who have completed at least the 25-week treatment period will be followed up for 16 weeks after completion of dosing (Visits 20 to 24) as per the Schedule of Activities in Section 2.

Safety and PK will be assessed throughout the study for each cohort.

Safety will be monitored by AEs, ECGs, vital signs (blood pressure and pulse rate), MRIs, neurological examinations, Columbia Suicide Severity Rating Scale (C-SSRS), and safety laboratory tests. In addition, blood samples for the assessment of immunogenicity will be taken at regular intervals throughout the dosing and follow-up periods. Each patient will have 1 screening (baseline) MRI prior to dosing with LY3303560, another after approximately 4 weeks, and then at approximately 12-week intervals thereafter as specified in the Schedule of Activities (Section 2), for the assessment of any potential imaging abnormalities. Tau imaging using flortaucipir F 18, cognitive and functional assessments (Neuropsychological Test Battery [NTB], the 14-item Alzheimer's Disease Assessment Scale – Cognition [ADAS-Cog₁₄], Mini-Mental State Examination [MMSE], digital clock drawing test [dCDT], and 24-question Alzheimer's Disease Cooperative Study/Activities of Daily Living scale adapted for MCI patients [ADCS-MCI-ADL24]), and cerebrospinal fluid (CSF) (via single lumbar puncture) will be assessed/obtained as detailed in the Schedule of Activities in Section 2. If scheduled on the same day, the cognitive/functional testing should be conducted before the lumbar puncture (LP), and the LP should occur no closer than 24 hours before dosing. The patient must be free from any

post-LP headache for at least 12 hours before dosing. If the LP is performed on a separate day before the cognitive testing, the cognitive/functional testing should be performed at least 24 hours after the LP, and the patient must be free from any post-LP headache for at least 12 hours before dosing (see Section 9.5.1 for detail on CSF sampling).

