7.4.2. Special Treatment Considerations

7.4.2.1. Premedication for Infusions

Premedication for the infusions is not planned. However, if an infusion reaction occurs, appropriate medication may be used as determined by the study investigator(s). If infusion reactions are observed, but review of the data suggests that dose escalation may continue, administration of paracetamol/acetaminophen (500 to 1000 mg) and/or an antihistamine, and/or methylprednisolone (or other corticosteroid) may be administered orally 30 to 60 minutes prior to the start of infusion for subsequent patients.

Any decision to implement premedication for infusions in subsequent cohorts will be made by the investigator(s) and sponsor and recorded in the study documentation, along with the dose-escalation decision.

Any premedications given will be documented as a concomitant therapy (see Section 7.7).

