9.2.1. Serious Adverse Events

An SAE is any AE from this study that results in one of the following:

- death
- initial or prolonged inpatient hospitalisation
- a life-threatening experience (that is, immediate risk of dying)
- persistent or significant disability/incapacity
- congenital anomaly/birth defect
- events considered significant by the investigator based upon appropriate medical judgment

Study site personnel must alert Lilly, or its designee, of any SAE within 24 hours of investigator awareness of the event via a sponsor-approved method. If alerts are issued via telephone, they are to be immediately followed with official notification on study-specific SAE forms. This 24-hour notification requirement refers to the initial SAE information and all follow-up SAE information.

Although all AEs are recorded in the CRF after signing informed consent, SAE reporting begins after the patient has signed informed consent and has received IMP. However, if an SAE occurs after signing informed consent, but prior to receiving IMP, AND is considered Reasonably Possibly Related to a study procedure then it MUST be reported.

Investigators are not obligated to actively seek AEs or SAEs in subjects once they have discontinued from and/or completed the study (the patient summary CRF has been completed). However, if the investigator learns of any SAE, including a death, at any time after a subject has been discharged from the study, and he/she considers the event reasonably possibly related to the study treatment or study participation, the investigator must promptly notify Lilly.

Pregnancy (maternal or paternal exposure to IMP) does not meet the definition of an AE. However, to fulfill regulatory requirements any pregnancy should be reported following the SAE process to collect data on the outcome for both mother and fetus.

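### Stopping criterion 3 excludes CSEs, so two related activity-impairing events that would force a stop need not do so when exactly one of them is also a CSE

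*Protocol*

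**What the plan says.** Protocol Section 7.4.1 lists four scenarios. If any one occurs, dosing at the current level and further escalation are discontinued.

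- **Criterion 1:** one or more patients with a related SAE. The SAE definition in Section 9.2.1 ends with a broad item, "events considered significant by the investigator based upon appropriate medical judgment".
- **Criterion 2:** "Two or more patients experience a clinically significant event (CSE) that is considered related to LY3303560 administration". A CSE is defined there as a "moderate-to-severe AE, abnormal clinical sign, or clinical laboratory finding that may pose a risk to the well-being of the subject".
- **Criterion 3:** two or more patients at a dose level with moderate or severe AEs that impair normal activities and are "considered related to LY3303560, but do not meet the CSE criteria".
- **Criterion 4:** "After the introduction of premedication in accordance with the protocol, 2 or more patients develop" infusion-related acute AEs of Grade 2 or higher that do not resolve. Section 7.4.2.1 says "Premedication for the infusions is not planned".

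The same section sets a presumption of relatedness: safety events "will be considered related to the IMP unless there is clear evidence that the event is not related". The SAP does not restate or change the criteria.

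**The concern.** Criteria 2 and 3 each need two patients, but they count separate sets of events. An AE that impairs activities and is also a CSE counts toward criterion 2 only. When one patient has such an event and another has an activity-impairing AE that is not a CSE, each criterion stands at one and neither is met. Had the first event been milder, criterion 3 would have been met.

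Safety is the primary objective, and Section 7.4.1 is the part of the protocol that takes some outcomes out of discretion. In this case a pair of events that would force a stop becomes discretionary because one event was judged to carry more risk. The outcome then turns on whether that AE may pose a risk to well-being, which is itself a judgement.

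**Working it through.** The documents state no operating characteristic for these criteria, so there is no figure to reproduce. The point rests on the logic in step 1; the probabilities only illustrate its size.

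**Step 1. Two patients at one dose level.** Let L be a related, activity-impairing moderate or severe AE that is not a CSE. Let C be the same kind of AE that is also a CSE but not an SAE.

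| Pair | Criterion 2 count | Criterion 3 count | Stop as written | Stop if criterion 3 also counts C |
|---|---|---|---|---|
| L, L | 0 | 2 | yes | yes |
| L, C | 1 | 1 | **no** | yes |
| C, C | 2 | 0 | yes | yes |

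**Step 2. When the gap applies.** All of these must hold:

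- The CSE is not a related SAE (criterion 1).
- The pair does not meet criterion 4, which operates only once premedication has been introduced.
- No second patient at any dose level has a related CSE, because criterion 2 has no dose-level limit.
- Neither patient also has, or later has, the other type of event over the 7 to 13 doses.

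The inversion is claimed only for a CSE that is itself an activity-impairing AE, not for a laboratory finding or clinical sign.

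**Step 3. One event type per patient.** Take n = 6 on LY3303560 (Protocol Section 5.1.3). The event rates are assumptions: pL and pC per patient, with p0 = 1 − pL − pC.

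- As written: P(stop) = 1 − [p0^6 + 6(pL + pC)p0^5 + 30·pL·pC·p0^4]
- With the exclusion deleted: P(stop) = 1 − [p0^6 + 6(pL + pC)p0^5]

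The term 30·pL·pC·p0^4 is the chance of exactly one L and one C, and it is the whole gap. With pL = pC = 0.10:

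- p0^6 = 0.8^6 = 0.2621
- 6 × 0.2 × 0.8^5 = 0.3932
- 30 × 0.1 × 0.1 × 0.8^4 = 0.1229
- As written: 1 − 0.7782 = 22.2%. Deleted: 1 − 0.6554 = 34.5% (from unrounded terms).

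| Patients affected | Share of events that are CSEs | As written | Exclusion deleted |
|---|---|---|---|
| 10% | 50% | 6.5% | 11.4% |
| 20% | 0% | 34.5% | 34.5% |
| 20% | 10% | 30.0% | 34.5% |
| 20% | 25% | 25.2% | 34.5% |
| 20% | 50% | 22.2% | 34.5% |
| 30% | 50% | 41.8% | 58.0% |

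**Step 4. Patients may have both types, independently.** Let T(p) be the chance that at least 2 of 6 patients have an event at rate p.

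- As written: 1 − [1 − T(p)]^2
- Deleted: T(1 − (1 − p)^2)

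At 10% for each type, T(0.10) = 0.1143. As written this gives 1 − 0.8857^2 = 21.5%; deleted it gives T(0.19) = 32.0%.

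| Rate of each type | As written | Exclusion deleted | Difference (points) |
|---|---|---|---|
| 5% | 6.4% | 10.9% | 4.5 |
| 10% | 21.5% | 32.0% | 10.5 |
| 20% | 57.1% | 69.9% | 12.9 (unrounded) |

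Steps 3 and 4 count criterion 2 within one level. Counting it across levels would narrow the gaps somewhat.

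**Step 5. Does the deletion cure it?** Let N be a related laboratory or sign CSE that does not impair activities. Each of 6 patients may have any combination of L, C and N, giving 8^6 = 262,144 states. There are 6 × 262,144 / 4 = 393,216 ways to change one patient's L to a C. As written, 60 of these turn a stop into no stop: 6 choices of that patient, 5 choices of the other patient with an L, and 2 for N present or absent. With the deletion none does, and no state that stops now ceases to stop. This checks the logic; it does not measure risk.

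**The case against.** The strongest counter-argument is that criterion 3 was meant as a fallback tier, catching pairs that fall short of criterion 2 rather than barring CSEs from the count. That reading would close the gap. However, the exclusion grammatically qualifies the AEs, and the CSE is defined event by event. If the fallback was intended, the deletion makes the text say so.

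A second argument is that a CSE will usually be reported as an SAE under the broad last item in Section 9.2.1, so criterion 1 would stop dosing. This will happen in some cases and narrows the gap. It cannot be the general rule: if every CSE were an SAE, criterion 2's threshold of two would never operate.

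Third, safeguards remain. Section 8.1 takes individual patients off drug for listed findings. Escalation needs agreement, with the more conservative sponsor view prevailing. Sections 8.2, 9.4.8 and 10.3.6 provide prompt reporting, suspension and ongoing review, and the sponsor team is unblinded at escalation reviews. All of this stands and limits the harm. None of it is a mandatory stop of a dose level for the mixed pair.

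Fourth, the rates are assumed, and a 50% CSE share gives the largest gap; at 20% affected and a 10% share it is 4.4 points (30 × 0.18 × 0.02 × 0.8^4). Appendix 6 also reports both cohorts well into dosing, with 9 subjects in each, and Section 3.3 gives 210 mg as the highest planned dose. Those points are fair: the figures do not estimate risk in this trial, and the practical benefit is mainly for continued dosing rather than escalation.

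**Conclusion.** The concern holds on the plain wording. One non-serious CSE that impairs activities plus one activity-impairing non-CSE event forces no stop, although two of the milder events do. The automatic rule is therefore not monotone in severity.

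The conclusion needs no event rate. Its size does: on the assumptions in the working, the mixed pair removes between about 4 and 16 percentage points of stopping probability at one level. The situation is narrow and discretion remains, but nothing in the protocol suggests that a milder pair was meant to be mandatory and a worse pair optional. The rule should be corrected.

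**What to change.** In criterion 3 of Protocol Section 7.4.1, strike the seven words after the comma in "considered related to LY3303560, but do not meet the CSE criteria". Every related moderate or severe AE that impairs normal activities then counts toward two patients at a dose level, whether or not it is a CSE. Leave criteria 1, 2 and 4 unchanged. Whether laboratory or clinical-sign CSEs should also count toward criterion 3 is an optional judgement for the sponsor; removing the inversion does not require it.

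The cost is a short protocol amendment, with no new data, visits or patients. The downside is earlier stopping in the mixed case: 4.5 to 12.9 points per level on the independent-type assumptions (5% to 20% for each type, 6 patients). Because relatedness is presumed and investigators are blinded, some of those added stops could be background events.

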7.4.2. Special Treatment Considerations

7.4.2.1. Premedication for Infusions

Premedication for the infusions is not planned. However, if an infusion reaction occurs, appropriate medication may be used as determined by the study investigator(s). If infusion reactions are observed, but review of the data suggests that dose escalation may continue, administration of paracetamol/acetaminophen (500 to 1000 mg) and/or an antihistamine, and/or methylprednisolone (or other corticosteroid) may be administered orally 30 to 60 minutes prior to the start of infusion for subsequent patients.

Any decision to implement premedication for infusions in subsequent cohorts will be made by the investigator(s) and sponsor and recorded in the study documentation, along with the dose-escalation decision.

Any premedications given will be documented as a concomitant therapy (see Section 7.7).

7.4.2.2. Management of Infusion Reactions

There is a risk of an infusion reaction with any biological agent; therefore, all patients should be monitored closely. Symptoms and signs that may occur as part of an infusion reaction include, but are not limited to, fever, chills, nausea, headache, bronchospasm, hypotension, angio-oedema, throat irritation, rash, pruritus, myalgia, and dizziness. In the event that a significant infusion reaction occurs, the following guidance should be followed:

- the IMP infusion should be slowed or stopped, depending on the symptoms/signs present:
 - if slowed, the infusion should be completed at the slower rate (at least 50% of the original infusion rate [for example, an infusion rate of 100 mL/hr becomes 50 mL/hr or slower]), as tolerated and documented in the CRF. The slower rate of infusion will be used for subsequent infusions for that patient
 - if stopped, no further attempts to administer the IMP for that patient will be made, and this will be documented in the CRF
- supportive care should be employed in accordance with the symptoms/signs.

Management of the infusion reaction should proceed according to the severity of the reaction as per the flowchart in [Appendix 5](#). This may include, but is not limited to, rescue medications such as diphenhydramine, adrenaline, and/or methylprednisolone.

Stored serum samples for possible exploratory immune safety laboratory testing (including but not limited to Beta tryptase, total immunoglobulin E, and immune complex testing) will be collected at time points indicated in the Schedule of Activities (Section 2).

Additionally, stored serum samples for possible exploratory immune safety laboratory testing should be collected approximately 60-120 minutes and 4-6 weeks after moderate or severe infusion reactions. Unscheduled samples may also be collected as needed.

Standardised clinical information from the infusion should be collected in the CRF.

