5.1.2. Dosing for all Cohorts

Patients will receive their study drug at the investigational site after all predose procedures have been completed and must be observed closely for at least 4 hours following each infusion of LY3303560 for the first 6 infusions. After the first 6 infusions, a minimum post-infusion observation time of 2 hours will be required for all subsequent infusions. If any patient shows symptoms of an infusion reaction, the observation time will be increased to a minimum of 8 hours for that infusion and all subsequent infusions.

If deemed necessary, for safety or feasibility reasons, patients may remain in the investigative site for a longer duration at the discretion of the investigator.

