7.1. Treatment Administered

This study involves a comparison of LY3303560 and placebo, with the planned doses of 70 and 210 mg. [Table LMDD.3](#) shows the treatment regimens. Detailed instructions for the preparation, handling, and administration of LY3303560 will be provided by the sponsor in a pharmacy binder.

The IMP will be administered as a slow IV infusion over at least 30 minutes.

The minimum time for close observation at the investigative site following dosing is 4 hours for the first 6 IV infusions and 2 hours for subsequent IV infusions. If any patient shows symptoms of an infusion reaction, the observation time will be increased to 8 hours for that infusion and all subsequent infusions. The site must have resuscitation equipment, emergency drugs, and appropriately trained staff available during dosing and while patients are under observation after dosing.

All IMP provided to the investigator will be stored in a secure location, and allocated and dispensed by appropriately trained, unblinded site personnel. The allocation and dispensing of the IMP will be fully documented and verified by a second person. Detailed records of the amounts of IMP received, dispensed and remaining at the end of the study will be maintained.

The actual time of all dose administrations will be recorded in the patient's case report form (CRF).

For purposes of scheduling, "dosing time" refers to the start of infusion.

Table LMDD.3. Treatments Administered

| Treatment Name | LY3303560 | Placebo |
|--|--|----------------------|
| Dosage Formulation | lyophilised powder in vial | liquid in vial |
| Unit dose strength(s)/Dosage Level(s) | each vial can deliver 90 mg LY3303560 | 0.9% normal saline |
| Route of Administration | intravenous infusion | intravenous infusion |
| Dosing instructions | Refer to pharmacy binder | |

The investigator's designee is responsible for:

- explaining the correct use of the IMP to the site personnel,
- verifying that instructions are followed properly,
- maintaining accurate records of IMP dispensing and collection,
- and returning all unused medication to Lilly or its designee at the end of the study.

Note: In some cases, sites may destroy the material if, during the investigative site selection, the evaluator has verified and documented that the site has appropriate facilities and written procedures to dispose of clinical trial materials.

7.1.1. *Packaging and Labeling*

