8.1. Discontinuation from Study Treatment

Patients will be discontinued from the IMP in the following circumstances:

- an SAE occurs that is related to study drug
- an SAE occurs during the infusion of the study drug, irrespective of causality; in this event, the drug is to be discontinued immediately. No re-dosing or completion of dosing is to be considered for that patient if the SAE is deemed to be related to study drug
- a clinically significant systemic hypersensitivity reaction occurs following administration of the IMP (for example, drug-related symptomatic bronchospasm, allergy-related oedema/angio-oedema, or hypotension), that requires parenteral medication, does not respond to symptomatic medication, or results in clinical sequelae or an anaphylactic reaction
- symptomatic or asymptomatic cerebral vasogenic oedema
- symptomatic cerebral microhaemorrhage or an increase in the number of cerebral microhaemorrhage >2 over baseline or such that the total number of microhaemorrhages is >4
- a clinically significant neurological finding
- an occurrence of suicidal ideation, as defined by a “yes” answer to Questions 4 or 5 on the Suicidal Ideation portion of the C-SSRS

Patients who discontinue the study drug early should complete all remaining scheduled visits (omitting dosing) if feasible or, at a minimum, the early discontinuation procedures as shown in the Schedule of Activities (Section 2).

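### Protocol Section 7.4.2.2 states the slowed infusion rate as a minimum, but its own example treats it as a maximum

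*Protocol*

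**What the plan says.** Under Protocol Section 7.4.2.2, a significant infusion reaction leads to slowing or stopping the infusion, depending on the symptoms and signs.

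- If slowed, the remainder is given at "at least 50% of the original infusion rate [for example, an infusion rate of 100 mL/hr becomes 50 mL/hr or slower", subject to tolerability and recorded in the CRF. The rate then carries forward: "The slower rate of infusion will be used for subsequent infusions for that patient".
- If stopped, "if stopped, no further attempts to administer the IMP for that patient will be made".

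Other sections touch on infusion rate or reactions, but none of their legible text gives a figure for the slowed rate.

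- Section 7.1 sets only the standard duration: "The IMP will be administered as a slow IV infusion over at least 30 minutes". It refers to a pharmacy binder for detailed administration instructions.
- Section 7.4.1, stopping scenario 4, counts reactions "that do not resolve with a reduced infusion rate and/or supportive care" and does not say how large the reduction must be.
- Section 7.4.2.2 also points to the Appendix 5 flowchart, whose content cannot be read in the public text.

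Section 7.4.2.2 is not among the sections that the legible Amendment (d) summary in Appendix 6 shows as revised. The sentence is current text.

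**The concern.** The rule and its example bound the rate from opposite sides. Taken alone, the words accept a slight slowing, such as 100 to 90 mL/hr, and exclude a cut to 25 mL/hr. The example does the reverse. The literal words therefore err in the less protective direction.

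The instruction is used at the bedside during a reaction, and its effect can repeat. With 7 doses plus up to 6 optional ones, a patient may receive 13 infusions, so a rate chosen after a reaction at dose 1 could apply to as many as 12 later ones.

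**Working it through.** No sample-size, power or error-rate figure is involved. The check compares the rule with its own example and then sizes the difference in minutes.

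**Inputs**

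- Original rate R0 = 100 mL/hr (example in Section 7.4.2.2).
- Standard infusion T0 = 30 min (the minimum in Section 7.1).
- For illustration only: slowed rates of 90, 75, 50 and 25 mL/hr, and a reaction halfway through the infusion. These are assumptions, not protocol values.

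**Step 1: the two bounds.** Let R be the slowed rate.

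- Words: R ≥ 0.50 × R0 = 50 mL/hr. Because the infusion is being slowed, R < 100, so 50 ≤ R < 100.
- Example: R ≤ 50 mL/hr.
- Both together: R = 50 mL/hr only.

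**Step 2: what the difference means in time.** Let f = R/R0. The second half of an infusion interrupted halfway takes 0.5 × T0/f = 15/f minutes. The whole interrupted infusion takes 15 + 15/f. A later infusion given entirely at the kept rate takes T0/f = 30/f minutes.

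| Slowed rate (mL/hr) | f | Allowed by | Remaining half (min) | Whole interrupted infusion (min) | Later full infusion (min) |
|---|---|---|---|---|---|
| 90 | 0.90 | words only | 15/0.90 = 16.7 | 31.7 | 30/0.90 = 33.3 |
| 75 | 0.75 | words only | 15/0.75 = 20 | 35 | 30/0.75 = 40 |
| 50 | 0.50 | both | 15/0.50 = 30 | 45 | 30/0.50 = 60 |
| 25 | 0.25 | example only | 15/0.25 = 60 | 75 | 30/0.25 = 120 |

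The minutes depend only on f and T0, not on the infused volume. Since 30 minutes is a minimum, a longer standard infusion scales every entry up in proportion.

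**Step 3: the corrected wording.** A reduction of at least 50% gives R ≤ 100 − 0.50 × 100 = 50 mL/hr, which is exactly the example.

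**Step 4: experience so far.** Appendix 6 reports no infusion reaction in 9 subjects in Cohort 1 and 9 in Cohort 2, 18 in all. Not all 18 appear to have had active drug: Section 3.3 describes nine patients at 70 mg, 7 on LY3303560 and 2 on placebo.

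**The case against.** The strongest reply is that the sentence corrects itself. It speaks of slowing, the phrase follows a reference to the slower rate, and a concrete example comes immediately after. A nurse choosing 75 mL/hr would have to disregard the only number supplied. The flowchart and the pharmacy binder may also state the rate correctly.

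Safeguards that do not depend on this phrase limit any harm:

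- The infusion can be stopped for good.
- Reaction symptoms mean that "the observation time will be increased to a minimum of 8 hours for that infusion and all subsequent infusions" (Section 5.1.2).
- Treatment ends if "a clinically significant systemic hypersensitivity reaction occurs following administration of the IMP" and the further conditions in Section 8.1 are met.
- Section 7.1 requires resuscitation equipment and trained staff.

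No misreading is documented, and the documents give no link from infusion minutes to patient risk.

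All of this stands as an argument for low severity. It does not remove the contradiction. Recovering the intent requires the reader to set aside the rule in favour of its example, and a correct flowchart or binder would leave this sentence inconsistent with itself and with them. The point should not be stretched to stopping scenario 4, which gives no size of reduction and applies only once premedication has been introduced. Section 7.4.2.1 says "Premedication for the infusions is not planned".

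**Conclusion.** The sentence is wrong as written: the words are a floor, the example is a ceiling, and they meet only at 50% of the original rate. The intended meaning, a cut of at least half, is clear from the example, so this is a drafting error of low severity and not a deliberate design choice.

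Its practical size is a later full infusion of 33 to 40 minutes at the illustrative rates that only the words allow, against 60 minutes or more under the example. That rests on the 30-minute minimum and the illustrative rates above. It affects no planned analysis, and no effect on dose escalation or stopping is claimed. Whether sites face real ambiguity in practice also depends on the flowchart and the binder, which could not be checked.

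**What to change.** In Section 7.4.2.2, replace the phrase before the bracketed example with *reduced by at least 50%, i.e. to no more than 50% of the original infusion rate*, and leave the example unchanged. Check that the Appendix 5 flowchart and the pharmacy binder agree. Issue the change by site clarification letter or in the next amendment. The cost is one phrase and that check; no analysis or data collection changes.
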